10.3. Concomitant treatments

Concomitant treatments are coded using the WHO-DRUG dictionary version 2022 Q1.

All treatments taken at least once from reference start date or appeared during the study will be summarised by Anatomical Therapeutic Class (ATC) and substance name. The number and percentage of patients in each category will be computed.

Patients will be counted only once within these ATC categories. They will be analysed on the FAS, by treatment group and overall.

Note: A medication which began strictly before reference start date and is on-going after reference start date is counted only in "previous medications" (see §8.2) and not in "concomitant medications".

AXIODIS CRO 21/47

10.4. Non-related adverse events

In the following paragraph, for a smoother reading:

- adverse events will be referred as AE;
- treatment-emergent adverse events will be referred as TEAE.

Adverse events are coded using the MedDRA dictionary version 25.0. They are classified by System Organ Class and Preferred Term.

For efficacy analyses, only non-related AEs are considered, i.e. adverse events with a relationship to study device equal to "not related". These analyses will be performed on the Safety Set and on the FAS, by treatment group and overall.

An adverse event will be considered as a treatment-emergent adverse event (TEAE) if:

- it was reported at least one day after screening;
- it was not present prior to the reference start date;
- it was present prior to the reference start date and worsened during the study (increase of intensity);
- it reappears after the reference start date (finished before the reference start date).

Missing or incomplete dates will be estimated as described in §6.4.4 in order to determine the TEAEs, but they will be presented as reported in CRF in the data listings. Generally, an adverse event for which the onset date is missing or incomplete and does not permit to identify the onset according to the date of the reference start date (i.e. missing onset day and month/year corresponding to the reference start date) will be considered as treatment-emergent.

Note: if the intensity/severity is missing, a conservative approach will be adopted and the intensity/severity will be considered as severe.

A given treatment-emergent adverse event (according to the MedDRA terminology) will be counted only once per patient. If a patient experienced several AEs in the same SOC/PT, the most severe intensity will be retained for this SOC/PT.

Summary of non-related adverse events

A summary table will be produced:

- number and percentage of patients with at least one non-related adverse event (AE);
- number and percentage of patients with at least one non-related AE leading to definitive study device discontinuation;
- number and percentage of patients with at least one non-related AE leading to definitive study discontinuation;
- number and percentage of patients with at least one serious non-related AE;
- number and percentage of patients with at least one non-related TEAE;
- number and percentage of patients with at least one serious non-related TEAE.

The number of non-related AEs of each category will also be provided in this table.

AXIODIS CRO 22/47

Statistical Analysis Plan Final version – August 09th, 2023

Analysis of non-related treatment-emergent adverse event

The number and percentage of patients with non-related TEAEs will be summarised by System Organ Class and Preferred term.

The number of non-related TEAEs of each category will also be provided in this table.

A listing of serious non-related AEs will be provided.

All non-related AEs leading to definitive discontinuation of the trial device or to definitive discontinuation of the study will be listed.

AXIODIS CRO 23/47

11. SAFETY

The following analyses will be performed on the Safety Set, by treatment group and overall.

11.1. Treatment and study duration

Study duration will be calculated according to the formula below:

Study duration (days) = Reference End Date - Reference Start Date + 1

Treatment duration will be calculated according to the formula below:

Treatment duration (days) = Device Stop Date - Reference Start Date + 1

Both will be described (see §6.2) on the Safety Set.

In addition, number and percentages of patients who stopped treatment before D8, at D8 morning, at D8 evening, ..., at D12 morning, at D12 evening and after D12 will be provided.

11.2. Incidents

For safety analyses, only incidents are considered, i.e. adverse events with a relationship to study device other than "not related".

Summary of incidents

A summary table will be produced:

- number and percentage of patients with at least one incident;
- number and percentage of patients with at least one incident leading to definitive study device discontinuation;
- number and percentage of patients with at least one incident leading to definitive study discontinuation;
- number and percentage of patients with at least one serious incident.

The number of incidents of each category will also be provided in this table.

Analysis of incident

The number and percentage of patients with incidents will be summarised by System Organ Class (SOC) and Preferred term (PT).

The number of incidents of each category will also be provided in this table.

A listing of serious incidents will be provided.

All incidents leading to definitive discontinuation of the trial device or to definitive discontinuation of the study will be listed.

AXIODIS CRO 24/47

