8.4 Secondary endpoints

A Cox survival regression model will be used to analyse the secondary endpoints of **duration of cold symptoms and of impact on quality of life**.

A multivariate Poisson regression model will be used to analyse the secondary endpoint related to the **number of days of use of conventional common cold medications** (overall and by therapeutic class).

A multivariate logistic regression model will be used to analyse the secondary endpoint related to the use (yes/no) of conventional common cold medications (overall and by therapeutic class).

-Safety: Adverse events/ incidents will be summarized by the number of occurrences, the number and percentage of patients by treatment group, classified by System Organ Class and Preferred Term as defined by MedDRA dictionary. Only treatment-emergent events will be analysed.

Frequency and percentage of patients with at least one reported adverse event/ incident / expected side effects will be tabulated by System Organ Class and by treatment group.

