14.2 Definitions

Incident means any malfunction or deterioration in the characteristics or performance of a device made available on the market, including use-error due to ergonomic features, as well as any inadequacy in the information supplied by the manufacturer and any undesirable side-effect (MDR 2017/745).

Serious incident means any incident that directly or indirectly led, might have led or might lead to any of the following: (a) the death of a patient, user or other person, (b) the temporary or permanent serious deterioration of a patient's, user's or other person's state of health, (c) a serious public health threat (MDR 2017/745).

Serious public health threat means an event which could result in imminent risk of death, serious deterioration in a person's state of health, or serious illness, that may require prompt remedial action,

and that may cause significant morbidity or mortality in humans, or that is unusual or unexpected for the given place and time (MDR 2017/745).

Expected and foreseeable side effects (MEDDEV 2 12-1 rev. 8)

They meet all the following criteria:

- Clearly identified in the manufacturer's labelling,
- Clinically well known as being foreseeable and having a certain qualitative and quantitative predictability when the device is used and performs as intended,
- Documented in the device master record, with an appropriate risk assessment, prior to the occurrence of the incident and,
- Clinically acceptable in terms of the individual patient benefit.

Adverse event means any untoward medical occurrence, unintended disease or injury or any untoward clinical signs, including an abnormal laboratory finding, in subjects, users or other persons, in the context of a clinical investigation, whether related or not related to the investigational device (MDR 2017/745).

Adverse or intercurrent events are graded as follows:

- Mild: Awareness of signs or symptoms but easily tolerated.
- Moderate: Uncomfortable enough to cause interference with usual activity.
- Severe: Incapacity with inability to work or do usual activity.

Serious adverse event (SAE) (MDR Article 2(58)):

Any adverse event that led to any of the following:

- a) death,
- b) serious deterioration in the health of the subject, that resulted in any of the following:
 - i. life-threatening illness or injury,
 - ii. permanent impairment of a body structure or a body function,
 - iii. hospitalisation or prolongation of patient hospitalisation,

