F_14_2_2_2_3_2_kmqol_fas.rtf	Figure	14.2.2.3.2	Kaplan-Meier graph for the duration of impact on Quality-of-Life by treatment group – Full Analysis Set	F4
T_14_2_2_3_1_cccmed_fas.rtf	Table	14.2.2.3.1	Impact of the treatment on the intake of conventional common cold medications – Full Analysis Set	T16
T 14 2 2 3 2 antibio fas.rtf	Table	14.2.2.3.2	Impact of the treatment on the intake of antibiotics – Full Analysis Set	T16
T_14_2_2_3_3_antipyr_fas.rtf	Table	14.2.2.3.3	Impact of the treatment on the intake of antipyretics – Full Analysis Set	T16
T_14_2_2_3_4_mucol_fas.rtf	Table	14.2.2.3.4	Impact of the treatment on the intake of mucolytics – Full Analysis Set	T16
T 14 2 2 3 5 decong fas.rtf	Table	14.2.2.3.5	Impact of the treatment on the intake of decongestants – Full Analysis Set	T16
T_14_2_2_3_6_antitus_fas.rtf	Table	14.2.2.3.6	Impact of the treatment on the intake of antitussives – Full Analysis Set	T16
T_14_2_2_3_7_cortico_fas.rtf	Table	14.2.2.3.7	Impact of the treatment on the intake of systemic and topical corticosteroids – Full Analysis Set	T16
T_14_2_3_cm_fas.rtf	Table	14.2.3	Concomitant treatments – Full Analysis Set	T5
T 14 2 4 1 1 1 ae saf.rtf	Table	14.2.4.1.1.1	Summary of non-related adverse events – Safety Set	T17
T 14 2 4 1 1 2 ae fas.rtf	Table	14.2.4.1.1.2	Summary of non-related adverse events – Full Analysis Set	T17

AXIODIS CRO 28/47

Final version – August 09th, 2023

File (BASICC)	Type	Number	Title	Mock
T_14_2_4_1_2_1_trtae_saf.rtf	Table	14.2.4.1.2.1	Non-related treatment-emergent adverse events by System Organ Class and Preferred Term – Safety Set	T18
T_14_2_4_1_2_2_trtae_fas.rtf	Table	14.2.4.1.2.2	Non-related treatment-emergent adverse events by System Organ Class and Preferred Term – Full Analysis Set	T18
L_14_2_4_2_1_1_sae_saf.rtf	Listing	14.2.4.2.1.1	Serious non-related adverse events – Safety Set	L3
L_14_2_4_2_1_2_sae_fas.rtf	Listing	14.2.4.2.1.2	Serious non-related adverse events – Full Analysis Set	L3
L_14_2_4_2_2_1_aedisct_saf.rtf	Listing	14.2.4.2.2.1	Non-related adverse events leading to definitive discontinuation of the trial device – Safety Set	L3
L_14_2_4_2_2_2_aedisct_fas.rtf	Listing	14.2.4.2.2.2	Non-related adverse events leading to definitive discontinuation of the trial device – Full Analysis Set	L3
L_14_2_4_2_3_1_aediscs_saf.rtf	Listing	14.2.4.2.3.1	Non-related adverse events leading to definitive discontinuation of the study – Safety Set	L3

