L_14_2_4_2_3_2_aediscs_fas.rtf	Listing	14.2.4.2.3.2	Non-related adverse events leading to definitive discontinuation of the study – Full Analysis Set	L3
SAFETY – INCIDENTS				
T_14_3_1_1_incsum_saf.rtf	Table	14.3.1.1	Summary of incidents – Safety Set	T17
T_14_3_1_2_incsocpt_saf.rtf	Table	14.3.1.2	Incidents by System Organ Class and Preferred Term – Safety Set	T18
L_14_3_2_1_sinc_saf.rtf	Listing	14.3.2.1	Serious incidents – Safety Set	L3
L_14_3_2_2_incdisct_saf.rtf	Listing	14.3.2.2	Incidents leading to definitive discontinuation of the trial device – Safety Set	L3
L_14_3_2_3_incdiscs_saf.rtf	Listing	14.3.2.3	Incidents leading to definitive discontinuation of the study – Safety Set	L3
PATIENTS DATA LISTINGS				
L_16_2_1_disc.rtf	Listing	16.2.1	Discontinued patients	NA
L_16_2_2_dv.rtf	Listing	16.2.2	Protocol deviations	NA

AXIODIS CRO 29/47

Study Number: LPH-2202

Statistical Analysis Plan BASICC Final version – August 09th, 2023

File (BASICC)	Туре	Number	Title	Mock
L 16_2_3_excl_eff.rtf	Listing	16.2.3	Patients excluded from the efficacy analysis	NA
L_16_2_4_1_dm.rtf	Listing	16.2.4.1	Demographic characteristics by patient	NA
L_16_2_4_2_1_mh.rtf	Listing	16.2.4.2.1	Medical history by patient	NA
L 16 2 4 2 2 mh coded.rtf	Listing	16.2.4.2.2	Medical history events (MedDRA V25.0)	NA
L_16_2_4_3_ie.rtf	Listing	16.2.4.3	Inclusion/Exclusion criteria	NA
L_16_2_4_4_forbidm.rtf	Listing	16.2.4.4	Past or concomitant forbidden medications and concomitant treatments for first symptoms of infectious rhinitis at enrolment / inclusion	NA
L_16_2_4_5_fever.rtf	Listing	16.2.4.5	Fever and body temperature	NA
L_16_2_5_1_sv.rtf	Listing	16.2.5.1	Dates of visits	NA
L_16_2_5_2_rand.rtf	Listing	16.2.5.2	Randomization and product unblinding	NA
L_16_2_5_3_compl.rtf	Listing	16.2.5.3	Compliance to treatment intake	NA
L_16_2_6_1_1_arssq.xml	Listing	16.2.6.1.1	Acute Rhinitis Symptoms Severity Questionnaire	NA
L_16_2_6_1_2_tte.rtf	Listing	16.2.6.1.2	Durations of common cold, of cold symptoms and of impacts on Quality-of-Life	NA
L_16_2_6_2_1_1 cm.rtf	Listing	16.2.6.2.1.1	Previous and concomitant medications by patient	NA
L 16 2 6 2 1 2 cm coded.rtf	Listing	16.2.6.2.1.2	Coded medications (WHO-DRUG 2022 Q1)	NA
L_16_2_6_2_intak.rtf	Listing	16.2.6.2.2	Intakes of common cold medications	NA
L_16_2_6_2_3_cm_end.rtf	Listing	16.2.6.2.3	Concomitant treatments at end of study / premature termination	NA

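### The SAP divides adverse events between safety and efficacy by device attribution and plans no summary of children with any event per arm, which Protocol 8.4 called for

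*SAP*

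**What the plan says.** Protocol 8.4, under safety, plans that adverse events and incidents "will be summarized by the number of occurrences, the number and percentage of patients by treatment group", coded by SOC and PT and limited to treatment-emergent events. It adds a tabulation, by SOC and arm, of patients having one or more adverse events, incidents or expected side effects. Neither sentence separates events by causality.

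The SAP divides them. Section 11.2: "For safety analyses, only incidents are considered, i.e. adverse events with a relationship to study device other than" not related. Section 10.4: "For efficacy analyses, only non-related AEs are considered, i.e. adverse events with a relationship to study device equal to" not related. For this second group, "These analyses will be performed on the Safety Set and on the FAS, by treatment group and overall".

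The output list in SAP 13.1 follows the same line. "Summary of incidents – Safety Set" (Table 14.3.1.1) stands in the safety block, and "Summary of non-related adverse events – Safety Set" (Table 14.2.4.1.1.1) stands in the efficacy block. The two classes come together only in patient listings 16.2.7.1 to 16.2.7.3.

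The word 'incident' also changes meaning. Protocol 14.2 begins: "Incident means any malfunction or deterioration in the characteristics or performance of a device made available on the market". It goes on to include use errors arising from ergonomics, inadequate manufacturer information and undesirable side effects. SAP 11.2 uses the word for a related adverse event only.

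**The concern.** The safety objective is systemic and local tolerance. In a blinded randomised trial, the comparison that answers it without anyone's judgement of cause is the proportion of children with any event in each arm. The SAP does not plan that comparison. Its safety section rests on investigator attribution, and attribution is difficult here. Protocol 5.2 expects no side effects, and local irritation from a nasal spray could resemble the runny nose, crusting, sneezing and sore throat that the questionnaire records as the disease.

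Two further consequences follow. A summary that the protocol planned is dropped without appearing in SAP 12, which does record the change to the primary analysis and to the symptom-duration rule. And a pump fault or use error that harms nobody is an incident under the protocol but enters no by-arm table under the SAP.

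**Working it through.** **The plan's own figure.** The documents state no safety rate, so there is none to reproduce. The only design figure is the sample size (Protocol 6.4, SAP 4): 100 per arm for d = 0.4, 80% power, 5% (two-sided, SAP 6.3.1). n = 2 × (1.960 + 0.842)² / 0.4² = 98.1, so 99 per arm. Power at 100 = Φ(0.4 × √50 − 1.960) = Φ(0.868) = 80.7%. It reproduces. It is used below only for the arm size.

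**Side by side.**

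| | Protocol 8.4 | SAP, related (11.2) | SAP, not related (10.4) |
|---|---|---|---|
| Filed under | Safety | Safety | Efficacy |
| Set | Safety population (8.1) | Safety Set | Safety Set and FAS |
| Summary table | All events | 14.3.1.1 | 14.2.4.1.1.1 (Safety Set) |
| SOC/PT table | All events | 14.3.1.2 | 14.2.4.1.2.1 (Safety Set) |
| Treatment-emergent limit on SOC/PT | Yes | None stated | Yes |
| Children with any event, by arm | Yes, by SOC | No | No |

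The two SOC/PT tables therefore apply different entry rules as well as different causality classes.

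**What can be added and what cannot.** Each event falls in one class, so the event counts in the two versions of mock T17 can be summed. Children cannot. Let a be the proportion of an arm with a related event, b the proportion with an unrelated event, and c the proportion with both:

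- any event = a + b − c, where c is not reported;
- c is at most min(a, b) and can be 0 when a + b ≤ 1;
- so max(a, b) ≤ any event ≤ a + b, a range of width min(a, b).

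Assumed counts per 100 children:

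| Related | Unrelated | Any event |
|---|---|---|
| 3 | 10 | 10 to 13 |
| 5 | 20 | 20 to 25 |
| 10 | 20 | 20 to 30 |
| 10 | 30 | 30 to 40 |

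Two arms that both show 10 and 20 could differ in any-event rate by anything from 20 − 30 = −10 to 30 − 20 = +10 points.

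**Reading the safety section alone.** Assume true any-event rates of 10% and 25%, 100 per arm, with a share s of affected children attributed to the device in each arm. Power = Φ[(Δ − 1.960 × SE₀) / SE₁], with SE₀ pooled and SE₁ unpooled.

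- s = 1: 10% v 25%; Δ = 0.15, SE₀ = 0.0537, SE₁ = 0.0527; power 80%.
- s = 0.5: 5% v 12.5%; Δ = 0.075, SE₀ = 0.0400, SE₁ = 0.0396; power 47%.
- s = 0.25: 2.5% v 6.25%; Δ = 0.0375, SE₀ = 0.0289, SE₁ = 0.0288; power 25%.

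The SAP plans no safety test. These figures show only how much weaker the contrast becomes in a related-only table read by itself.

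**The case against.** The strongest reply is that the information is divided, not discarded. The unrelated events have their own summary, SOC/PT table and listings on the Safety Set by arm. Event totals can be added by hand. For serious events and discontinuations, mock L3 carries patient, treatment and causality for both classes, so exact all-cause patient counts can be rebuilt. All of this stands.

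A reader might therefore infer too much in three ways.

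- **That tolerance by arm cannot be read without attribution.** The documents do not support this. A device effect called unrelated would still appear as an imbalance between arms in Table 14.2.4.1.2.1, provided it is treatment-emergent. It would be filed under efficacy, not hidden. Investigators are also blinded (Protocol 7.1.2).
- **That harmless device problems go unreported.** Protocol 14.3 puts all incidents in the eCRF, and 14.4.1 and 14.5.1 send them through vigilance. Only the by-arm summary is missing.
- **That a large effect is being obscured.** No event rate is stated. With no side effects expected, incidents may be so few that the unrelated-event summary nearly equals the all-cause one.

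It can also be argued that the efficacy label is reasonable, because the protocol collects adverse events pertinent to the cold, and these may reflect the course of the disease. But Protocol 7.1.4 and 8.4 place them under safety, and the label does not supply the missing count.

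**Conclusion.** The point holds as a reporting gap and an unrecorded departure from the protocol. It does not show lost data or a biased test. Four things are established from the text:

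- the safety section is limited to device-attributed events;
- no planned summary gives children with any event per arm, overall or by SOC/PT;
- the two SOC/PT tables do not share a treatment-emergent rule;
- incidents that are not adverse events have no by-arm summary.

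The size of the gap is the smaller of the two patient percentages in each arm: 3 points at assumed rates of 3% and 10%, 10 points at 10% and 20%, and negligible if incidents are rare. Every rate used here is an assumption. The any-event count could be rebuilt from the listings after the fact, but that would be an unplanned analysis. The difference in treatment-emergent rule probably matters little, since an event attributed to the device must follow first use. Even a combined table would cover only events that the investigator validated as pertinent (Protocol 7.4.1, 14.3).

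**What to change.** 1. Add to SAP section 11, on the Safety Set by arm, all-causality treatment-emergent tables giving children and events: any event, serious events, events leading to discontinuation, and SOC/PT. Show device-related events as a subset of each.
2. Apply one treatment-emergent rule to both classes, as Protocol 8.4 requires. State how the conditions listed in SAP 10.4 combine, because one asks for reporting at least a day after screening, while Protocol 7.4.1 puts first use on the evening of Day 1.
3. Add a by-arm count of incidents in the Protocol 14.2 sense that are not adverse events. Use a different term for related adverse events.
4. Record the split, and any remaining change of definition, in SAP 12.

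The section 10.4 tables can stay as they are. The cost is some SAP wording and a few extra tables from data that the protocol already sends to the eCRF.

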12. CHANGES IN THE CONDUCT OF THE STUDY OR PLANNED ANALYSIS

The planned analysis in the protocol to assess the primary objective (multivariate ANCOVA model of the AUC on global score of ARSSQ during the first eleven days of the study) has been replaced by the comparison of the means of the AUC on global score of ARSSQ during the first eleven days of the study between treatment groups. The multivariate ANCOVA has been put among secondary analyses.

This change has no impact on the relevance of the sample size calculation since the primary endpoint is the same as planned in the protocol.

Moreover, since several patients still reported having symptoms while they reported they did not feel sick anymore at the question 1 during at least the two last days of completion of the ARSSQ, their positive answers to the cold symptoms' items have been considered as non-significant. Consequently, the question 1 has been taken into account in addition to the corresponding items to determine the end of the cold symptoms' duration, however only on the condition that the last days of completion were consecutive.

If the last days of completion were not consecutive, positive answers to cold symptoms' items are still considered as symptomatic, even if the two last answers to the question 1 are negative. The symptom ends at the last symptomatic day if the patient reported the absence of this symptom at least twice and consecutively after this day. Otherwise, the duration of the symptom is censored at D18 or at the end of the study, whichever occurs first.

The same change has been applied to compute the duration of impact on QoL.

AXIODIS CRO 25/47

